3.3.1 MDX-010

There will be no intra-patient dose modifications of MDX-010. Patients will discontinue treatment with MDX-010 if they experience an adverse event felt to be possibly or probably related to MDX-010 antibody that meets the following criteria:

- A patient who requires systemic steroid therapy for any reason will not receive further treatment with MDX-010 but will be followed until off study criteria are met.
- Any infusion related reaction of \geq grade 3. Infusion related reactions are defined as acute reactions that develop and resolve within 48 hours of the start of an infusion. This includes reactions that are responsive to therapy within that time frame except for Grade 3 fever that resolves within 48 hours. Exclusions to discontinuing therapy will be made in the presence of an objective response when the toxicity resolves prior to the next infusion.
- Any autoimmune toxicity of $>$ grade 2 that has the potential to be life threatening with continued antibody administration and is not associated with a potential therapeutic response, except rash, vitiligo or asymptomatic autoantibody detection. An autoimmune reaction is defined as an inflammatory process that compromises the function of any organ and is not attributable to another etiology.
- Any autoimmune toxicity (any grade) that does not resolve by the time that additional dosing with MDX-010 is considered. Patients may delay subsequent doses in a course by up to a maximum of 3 weeks while awaiting resolution of an autoimmune toxicity.
- Uveitis or episcleritis that is symptomatic (causing eye pain, photosensitivity, or blurred vision)
- Exclusions to these criteria include inflammation of $<$ grade 4 that is attributable to a local anti-tumor reaction that could potentially be a therapeutic response. This

includes inflammatory reactions at the site of tumor resection or in draining lymph nodes, or in sites suspicious for metastasis.

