3.4.2.9. PBMC (peripheral blood mononuclear cells) sample

Peripheral blood mononuclear cells (PBMC) will be isolated and purified from samples obtained at baseline and after every course, by drawing 75 ml of blood at these times according to the schedule. In addition, 5 ml of serum will be obtained and stored at baseline and at the time of each blood draw.

Schedule								
	On-Study Evaluation						Follow up	
Visit	2	3	4	5	6	7 ⁷		
Day	0	21 ±2d	42 ±2d	63 ±2d	84 ±2d	105 ±4d		Variable ¹
MDX-010 Dose (mg/kg)	3	3	3	3	3	3		
Adverse events	X	X	X	X	X	X		X
	X	X	X	X	X	X		X
Physical examination	X	X	X	X	X	X		X
Assessment for ocular symptoms	X	X	X	X	X	X		X
Vital signs ³	X	X	X	X	X	X		X
Performance Status	X	X	X	X	X	X		X
Ophthalmologic examination**					X			
Pulmonary Function Testing ²								
Diagnostic imaging					X	X		X
Hematology		X	X	X	X			X
Biochemistry		X	X	X	X	X		X
Urinalysis					X			
Urine pregnancy test ⁴	X	X	X	X		X		
ANA ⁵					X			
Antithyroglobulin					X			
Thyroid Function Test ⁶					X			
Blood sample					X			
Infusion of MDX-010	X	X	X	X		X		
Disease Response					X			X

- ¹ 3-month intervals for 1 year, 6-month intervals for 2 years, and 12-month intervals until recurrence of disease
 - ² •²PFT's will be performed if patients develop any clinical sign or symptom suggestive of deterioration of pulmonary function.
 - ³ Vital signs will be monitored every 30 minutes for the duration of the MDX-010 infusion and for one hour following infusion completion, and then routinely unless otherwise indicated.
 - ⁴ A negative urine pregnancy test will be confirmed prior to each dose of MDX-010 in women of child-bearing potential.
 - ⁵ If ANA positive, perform the ENA. If ENA positive, perform the tests indicated in Section 3.4.2.5.
 - ⁶ If abnormal, run full thyroid panel, including Free T3 and Total T4.
 - ⁷ Subsequent Courses (after the first course) will receive MDX-010 every 3 weeks X 4 if the patient is stable or has a partial or mixed response with toxicities of grade 1 or less after the 1st course. Subsequent courses for patients with stable, partial or mixed response, or for patients with complete or partial responses that have relapsed, may be offered.
- ** Additional ophthalmologic exams will be performed if the patient experiences ocular symptoms.

3.6 Off Study Criteria:

Patients may be removed from the study in the following situations:

- Protocol violations
- Disease progression
- Subject withdrew consent
- Lost to follow up
- Death

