4.3 Treatment of \geq Grade III Autoimmune Adverse Events

For **skin-related** \geq Grade III autoimmune toxicity, including severe generalized pruritis or rash, symptomatic treatment will be given. The types of therapy may include local skin care, antihistamines, or corticosteroids (which can be local/topical or systemic) as clinically indicated. At the discretion of the principal investigator, patients experiencing a skin-related autoimmune toxicity \geq Grade III who have not required systemic steroids may resume MDX-010 once the skin symptoms improve (see Section 3.3.1). Patients who require systemic steroid therapy will not receive further treatments with MDX-010.

Treatment for **non-skin-related** autoimmune adverse events \geq Grade III will be prescribed as clinically indicated depending on the severity of the symptoms and/or physical manifestations. Treatment may include oral, locally-delivered (e.g., per rectum) or i.v. steroids and/or other supportive care. No further doses of MDX-010 will be given once a patient develops a \geq Grade III non-skin-related autoimmune adverse event attributable to the investigational agents or if the patient requires systemic steroid therapy.

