2.3.6 Study Flow Chart

Table 2: Schedule of Assessments, Day 0 through Termination of Participation

Schedule	On-Study Evaluations					Follow-up Variable ^{1,8}
	2	3	4	5	6 ⁷	
Visit	2	3	4	5	6 ⁷	
Day	0	21 ±2d	42 ±2d	63 ±2d	84 ±2d	
MDX-010 Dose (mg/kg)	3	3	3	3	3	
Adverse events	X	X	X	X	X	X
████████████████████	X	X	X	X	X	X
Physical examination	X	X	X	X	X	X
Assessment for ocular symptoms	X	X	X	X	X	X
Vital signs ³	X	X	X	X	X	X
Performance Status	X	X	X	X	X	X
Ophthalmologic examination**					X	
Pulmonary Function Testing ²					X	X
Diagnostic imaging					X	X
Hematology		X	X	X	X	X
Biochemistry (including amylase and lipase)		X	X	X	X	X
Urinalysis					X	X
Pregnancy test ⁴	X	X	X	X	X	
ANA ⁵					X	
Antithyroglobulin					X	
Thyroid Function Test ⁶					X	
Blood (PBMC) sample					X	
PK sample ⁹	X			X		
HAHA sample ¹⁰	X				X	
Infusion of MDX-010	X	X	X	X	X	

Disease Response					X	X
1: 3-month intervals for 1 year, 6-month intervals for 2 years, and 12-month intervals until recurrence of disease. 2: PFT's will be performed if subjects develop any clinical sign or symptom suggestive of deterioration of pulmonary function.. 3: Vital signs will be monitored every 30 minutes for the duration of the ipilimumab infusion and for one hour following infusion completion, and then routinely unless otherwise indicated. 4: A negative pregnancy test will be confirmed prior to each dose of ipilimumab in women of childbearing potential; refer to section 2.2.7 C of the protocol. 5: If ANA positive, perform the EBA. If ENA positive, perform the tests indicated in Section 3.4.2.5 of the protocol. 6: If abnormal, run full thyroid panel, including Free T3 and Total T4. 7: A second course of 4 additional infusion ipilimumab (every 3 weeks x 4) may be given if the subject shows toxicities of grade 1 or less after the first course. 8: Up to 2 Subsequent courses of 4 infusions each ipilimumab (every 3 weeks x 4) may be given to subjects with complete or partial responses that have relapsed (PD). 9: For 5 subjects in each group, blood samples (5 mL) for the analysis of plasma concentrations of ipilimumab will be drawn prior to the 1 st and 4 th doses of ipilimumab and again at 1 hour post-infusion. 10: For 5 subjects in each group, blood samples (1 mL) for the analysis of HAHA will be drawn at baseline and 3 weeks after the last infusion of the subject's last course of treatment. **: Additional ophthalmologic exams will be performed if the subject experiences ocular symptoms						

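### Protocol Section 3.3.1 requires an autoimmune toxicity to have resolved before further MDX-010, but Section 4.3 and schedule footnote 7 permit dosing while it persists

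*Protocol*

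**What the plan says.** **Protocol 3.3.1.** The lead-in reads: "Patients will discontinue treatment with MDX-010 if they experience an adverse event felt to be possibly or probably related to MDX-010 antibody" and then lists criteria. Two of them concern autoimmune toxicity in general.

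- The third bullet is a severity trigger. It covers events above grade 2 that could become life threatening with continued antibody and are not tied to a possible therapeutic response, "except rash, vitiligo or asymptomatic autoantibody detection".
- The fourth bullet is a persistence trigger: "Any autoimmune toxicity (any grade) that does not resolve by the time that additional dosing with MDX-010 is considered". It adds: "Patients may delay subsequent doses in a course by up to a maximum of 3 weeks while awaiting resolution of an autoimmune toxicity". It does not repeat the exceptions of the third bullet.

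The closing bullet of 3.3.1 exempts only inflammation below grade 4 that is attributed to a local anti-tumor reaction.

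**Protocol 4.3.** At the principal investigator's discretion, patients with a skin-related autoimmune toxicity of Grade III or more who did not need systemic steroids "may resume MDX-010 once the skin symptoms improve (see Section 3.3.1".

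**Protocol schedule table, footnote 7.** Further courses are given "if the patient is stable or has a partial or mixed response with toxicities of grade 1 or less after the 1st course".

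**SAP 2.3.6, footnote 7** (same condition in SAP 2.2.1, Table 1, footnote 3). A second course "may be given if the subject shows toxicities of grade 1 or less after the first course".

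**The concern.** Section 3.3.1 asks for resolution. Section 4.3 asks for improvement, and footnote 7 asks for grade 1 or less. A toxicity can improve, or fall to grade 1, without resolving. Where more than one of these rules covers a patient, they can give opposite instructions.

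The first thing at stake is safety: whether a patient with ongoing autoimmune toxicity receives more antibody would depend on which page the site consulted. The second is the data that the SAP still reports. Reasons for discontinuation (SAP 5.4) and total dose and number of doses (SAP 5.6) would partly reflect the rule each investigator applied. The treatment-emergent window in SAP 5.9.1 runs 70 days from the last dose, so it would move too. That last effect is confined to events not judged drug-related, because related events count whatever their start date.

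**Working it through.** No arithmetic is involved in the conflict itself. The check is to list the states a patient can be in when more MDX-010 is considered, apply each rule, and see where they disagree. All cases assume that the event is felt to be possibly or probably related, that no systemic steroids were needed, and that the local anti-tumor exclusion does not apply.

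| Case | 3.3.1, fourth bullet | 4.3 | Footnote 7 | Agree? |
|---|---|---|---|---|
| 1. Within a course: skin toxicity reached Grade III, improved to grade 1 or 2, still present after the 3-week delay | Discontinue | May resume | Not applicable | **No** |
| 2. After course 1: grade 1 autoimmune rash still present, never above grade 2, stable disease | Discontinue | Not applicable | Further course allowed | **No** |
| 3. Within a course: rash never above grade 2, still present after the delay | Discontinue | Not applicable | Not applicable | Yes, only one rule applies |
| 4. Within a course: non-skin autoimmune toxicity of Grade III or more, unresolved | Discontinue | No further doses | Not applicable | Yes |
| 5. After course 1: autoimmune toxicity still at grade 2, never higher | Discontinue | Not applicable | Condition not met | Yes |
| 6. After course 1: low-grade autoimmune toxicity fully resolved, stable disease | Not triggered | Not applicable | Further course allowed | Yes |

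The disagreement is confined to cases 1 and 2.

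- **Case 1** turns on improvement versus resolution. It begins before the 3 weeks run out: at the next scheduled dose Section 3.3.1 would have the patient wait, while Section 4.3 would allow dosing on improvement.
- **Case 2** turns on grade 1 or less versus resolution. The 3-week delay is written for doses inside a course, so it does not settle what happens between courses.

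A separate check concerns the third and fourth bullets of 3.3.1. They are cumulative: exemption from the severity trigger is not permission under the persistence trigger. A persistent rash exempt from the third bullet and caught by the fourth is therefore not a contradiction. What is missing is a statement of whether the exceptions were meant to reach the fourth bullet.

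**The case against.** The best defence is that the rules can be harmonised.

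- **Section 4.3 is permissive and cites 3.3.1**, so it may be subject to it. That is possible. But the word for improvement would then do no work, and the citation could as well point to the rash exception in the third bullet. The text does not say which.
- **Footnote 7 may be a further necessary condition**, applied on top of 3.3.1. Also possible, but neither the protocol footnote nor the SAP footnotes link to 3.3.1.
- **The fourth bullet may be meant only within a course**, since its delay clause is. Its main clause has no such limit, and a new course is additional dosing.
- **A mild rash may not be an autoimmune toxicity at all**, because "An autoimmune reaction is defined as an inflammatory process that compromises the function of any organ and is not attributable to another etiology". Against this, the third bullet needs an exception for rash, vitiligo and symptom-free autoantibodies only if they would otherwise count, and a symptom-free antibody compromises no organ. Section 4.3 also classes rash as autoimmune, though only when severe, so the low-grade case stays open.

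What stands is the narrow reach. A rash that never exceeded grade 2 meets the conflict only through footnote 7. Non-skin events of Grade III or more are stopped under 4.3 as well. The two conflicts arise at different decision points and should not be run together: a patient permanently stopped mid-course under 3.3.1 never reaches the footnote 7 decision.

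The SAP footnotes also deserve caution. The SAP describes HAHA and PK sampling, up to 2 additional courses after relapse, and a second course after progression, none of which is in the supplied protocol. It may follow another protocol version.

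**Conclusion.** Two pairs of rules conflict in current text: 3.3.1 against 4.3 within a course, and 3.3.1 against footnote 7 before a new course. The scope of the third-bullet exceptions is unstated, which is a gap rather than a third conflict. The conclusion assumes that the three provisions carry equal authority, since the protocol ranks none above another. Its size cannot be given, because the documents do not report how many patients had an autoimmune toxicity that improved without resolving.

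Two stronger inferences are tempting and are not supported.

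- **That the conflict could change a cohort's conclusion**, since the design turns on 2 versus 1 responders in 21 and 5 versus 4 in 41. Stopping drug does not remove a patient from response assessment: best response runs from the start of treatment to progression (Protocol 5.3.1.3), and toxicity is not among the off-study criteria (3.6). Nothing shows that the disputed doses would make or lose a confirmed response. SAP 5.10 reports no responses in the first stage, so one more would give 0 + 1 = 1, still within the stopping rule of 0 or 1 in 21. Efficacy is not analysed (SAP 5.8).
- **That the affected patients are those most likely to respond.** The link between autoimmunity and response that the protocol cites comes from melanoma and renal cell cancer, and the study design text speaks of severe autoimmunity. Neither establishes anything about a residual low-grade rash in pancreatic cancer.

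The point is worth correcting for safety and for consistent data.

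**What to change.** 1. Reconcile Protocol 3.3.1, 4.3 and schedule footnote 7 into one stated criterion for the state an autoimmune toxicity must reach before the next dose and before a new course. The sponsor and investigator decide what it is; this review takes no view.
2. State whether the exceptions in the third bullet of 3.3.1 also apply to the fourth.
3. Have 4.3 and footnote 7 refer to that rule instead of restating it, and say whether the grade limit in footnote 7 adds to it or replaces it.
4. Align the SAP footnotes (Table 1 footnote 3, Table 2 footnote 7) with the governing protocol version, and name that version.
5. The SAP records the trial as terminated. If dosing has ended, the study report should say which rule was applied and identify any patient re-dosed with an unresolved autoimmune toxicity. The planned dosing and adverse event listings (3.1, 7.1, 7.2) are the natural source.

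The cost is amendment wording, small SAP footnote corrections and a short cross-check of listings already planned. No visits or patients are added.

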2.2.4 Ophthalmologic examination

Ophthalmologic examination will be performed at baseline and at the end of each course and if any ocular symptoms develop. Visual acuity evaluations will be performed during each such assessment. All reports will be filed with the patient's source documentation. Appropriate CRF's must be completed.

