3.4.1.5. Assessment of adverse events

3.4.1.6. Assessment of concomitant medications

3.4.2 Assessment prior to each new course

3.4.2.1. Physical examination

3.4.2.2. Assessment of performance status

3.4.2.3. Diagnostic imaging appropriate to tumor evaluation, using the same imaging modality, method of assessment, or technique used for baseline evaluation. Repeat diagnostic imaging will be performed after each course of therapy (approximately day 55).

3.4.2.4. Ophthalmologic examination at the completion of course 1 and again if any ocular symptoms develop, including retinal pigmentation changes. Visual acuity will be performed during each assessment.

3.4.2.5. Autoimmune Panel:

Antithyroglobulin antibody

ANA, if positive perform the ENA, if ENA positive, perform the following tests (If negative, then a sample of serum will be stored for subsequent testing in the event that the ANA becomes positive at a later date):

- Anti-phospholipid antibody
- Anti-neutrophil cytoplasm antibody
- CH50
- Anti-DNA antibody
- Anti-SSA antibody
- Anti-SSB antibody
- Rheumatoid factor (RF)

3.4.2.6. Thyroid function tests, as defined for baseline in Section 2.2.12.

3.4.2.7. Hematology (Hemoglobin, Hematocrit, Complete blood cell count with differential and platelet count (direct) and sedimentation rate, and biochemistry testing (Albumin, Alkaline phosphatase, ALT, AST, Bilirubin (total and direct), Calcium Chloride, Bicarbonate, Creatinine, Glucose, Lactate dehydrogenase (LDH), Potassium, Sodium, Total protein, Urea nitrogen (BUN), Uric acid)

3.4.2.8. Pulmonary function tests will be conducted if patients develop any clinical sign or symptom suggestive of deterioration of pulmonary function.

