4.5 Treatment of Any Ocular Toxicity

Patients who report any visual symptom will be immediately referred to an ophthalmologist. Upon evaluation by the ophthalmologist, the patient will be treated as deemed appropriate by the ophthalmologist, including peri-ocular steroid injections or steroid eyedrops if necessary. No further doses of MDX-010 will be given once a patient experiences an autoimmune ocular toxicity attributable to the investigational agents.

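### Protocol Sections 3.3.1 and 4.5 set different ocular stopping rules for MDX-010, and they conflict for mainly low-grade autoimmune eye events that resolve before the next dose

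*Protocol*

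**What the plan says.** Protocol Section 3.3.1 lists the adverse events that end treatment. Three of its items can reach an eye event:

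- The ocular item: "Uveitis or episcleritis that is symptomatic (causing eye pain, photosensitivity, or blurred vision".
- The non-resolution item: "Any autoimmune toxicity (any grade) that does not resolve by the time that additional dosing with MDX-010 is considered". It comes with an allowance: "Patients may delay subsequent doses in a course by up to a maximum of 3 weeks while awaiting resolution of an autoimmune toxicity".
- The item for autoimmune toxicity above grade 2, which applies only where the toxicity "has the potential to be life threatening with continued antibody administration and is not associated with a potential therapeutic response".

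Protocol Section 4.5, on ocular toxicity, ends with a rule of its own: "No further doses of MDX-010 will be given once a patient experiences an autoimmune ocular toxicity attributable to the investigational agents".

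Three other places bear on the same decision. Section 4.3 bars further MDX-010 after an attributable non-skin autoimmune event of grade III or higher. Footnote 7 of the protocol schedule makes a second course depend on toxicity no higher than grade 1 after the first, together with stable disease or a partial or mixed response. Section 2.2.4 sets the eye examinations: "Ophthalmologic examination will be performed at baseline and at the end of each course and if any ocular symptoms develop".

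Neither 3.3.1 nor 4.5 refers to the other on when an eye event ends treatment, and no text says which prevails.

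**The concern.** One section attaches a diagnosis and a symptom condition to its ocular stop; the other attaches neither. An investigator who works from the list in 3.3.1 and one who works from 4.5 can therefore decide differently about the same patient.

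The situation is foreseeable. Eye examinations are scheduled at the end of a course whether or not the patient has symptoms, and that is when the next course is considered. The local steroids named in 4.5 are not systemic, so their use does not trigger the systemic-steroid stop in 3.3.1.

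At stake are whether an individual patient is dosed again after an autoimmune eye event, and how a discontinuation for an eye event, or its absence, should be read in a safety report that is now the whole of the planned analysis (SAP Section 5.10).

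**Working it through.** No planned figure depends on this point, so the check is a comparison of the rules case by case. Take an eye event that is autoimmune, meets the attribution wording of both sections and needs no systemic steroid.

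| Eye event | Section 3.3.1 | Section 4.5 | Result |
|---|---|---|---|
| (a) Uveitis or episcleritis with symptoms | Stop (ocular item) | Stop | Agree |
| (b) Any diagnosis, any grade, not resolved at the dosing decision | Stop (non-resolution item) | Stop | Agree |
| (c) Grade III or higher, resolved, not covered by (a) | Stop only if the life-threatening item is met | Stop | 4.3 already stops, so 4.5 adds nothing |
| (d) Grade 1-2, resolved, not uveitis or episcleritis | No item stops | Stop | Conflict |
| (e) Grade 1-2, resolved, uveitis or episcleritis without symptoms | No item stops | Stop, read literally | Conflict on that reading |

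The conflict specific to 4.5 is confined to rows (d) and (e).

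**Second course.** Footnote 7 narrows both rows. If its limit refers to the worst toxicity during course 1, only grade 1 events remain in conflict. If it refers to toxicity still present after course 1, a resolved grade 2 event also remains. The footnote does not say which. It does not govern later doses within a course that has already started.

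**Timing.** As the protocol schedule reads, the eye examination is at day 84 and the next marked infusion at day 105, so a finding has 105 - 84 = 21 days, or 3 weeks, in which to clear. In SAP Table 2 the examination and the infusion are both marked at the day 84 visit. A finding made there is unresolved when that dose is considered, so 3.3.1 withholds the dose as well.

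**Size for one patient.** A course is 4 infusions. For a row (d) or (e) event found at the end of course 1, Section 4.5 allows 0 further infusions. Section 3.3.1 leaves up to 4, if course 2 is otherwise permitted. The difference is at most 4 - 0 = 4. For an event after the first infusion of a course, up to 4 - 1 = 3 infusions of that course are in question, and footnote 7 does not apply to them.

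**Number of patients.** The documents give no rate of autoimmune ocular events, so this cannot be computed.

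**The case against.** The strongest reply is that the two sections are cumulative. Section 3.3.1 does not call its list exhaustive and does not require redosing after an eye event. Section 4.3 points to 3.3.1, and the accrual-halt paragraph that follows the 3.3.1 list points to Sections 4.0 to 4.5, so they are meant to be read together. A site obeying both would stop. This shows that the protocol can be followed without breaching either section. But on that reading the symptom condition in 3.3.1 does nothing for attributable events, and an investigator cannot tell whether it was meant to have effect.

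The second reply concerns events without symptoms. Section 4.5 opens with patients who report a visual symptom, and 3.3.1 says: "An autoimmune reaction is defined as an inflammatory process that compromises the function of any organ and is not attributable to another etiology". A silent finding may fall outside one or both. This stands as a real doubt about row (e), since the stopping sentence of 4.5 carries no such limit but its context might. It does not touch row (d): a symptomatic event of another diagnosis that impaired vision and then cleared fits the opening of 4.5 and the definition in 3.3.1.

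A reader might infer stronger claims that the documents do not support:

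- *That 3.3.1 stops treatment only for symptomatic uveitis or episcleritis.* Its non-resolution item also reaches eye events of any diagnosis and grade.
- *That any finding at a scheduled eye examination leads to opposite dosing decisions.* A finding that persists to the dosing decision stops treatment under both sections.
- *That the conflict specific to 4.5 exists at every grade.* Section 4.3 covers grade III and above.
- *That harm to sight or distorted ocular discontinuation rates follow.* There is no event rate to support the first, and the SAP plans no table of ocular discontinuations. It plans overall reasons for discontinuation (Section 5.4) and an ophthalmologic table (Table 5.3).

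**Conclusion.** The inconsistency is real but narrow. Sections 3.3.1 and 4.5 give different answers for attributable autoimmune ocular events that have resolved by the next dosing decision and are either not uveitis or episcleritis (firm) or without symptoms (on a literal reading of 4.5). The disagreement specific to 4.5 lies mainly at grades 1 and 2, and footnote 7 reduces it further for a second course. For an affected patient at the end of course 1, the rules differ by up to 4 infusions; the number of such patients is unknown.

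The conclusion assumes that no systemic steroid was needed, that the attribution wording of both sections is met, and, for the figure of 4, that every other condition for course 2 is satisfied. It takes no position on which rule is clinically right. Because it concerns when dosing ends for safety, and is cheap to settle, it should be corrected. The SAP reports the trial as terminated, so the practical value now lies mostly in reading the safety data and in any later use of this protocol text.

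**What to change.** Reconcile the ocular item of Section 3.3.1 with the last sentence of Section 4.5 so that both use one definition of the eye event that ends MDX-010. The definition should state which diagnoses are covered, whether symptoms are required, and whether resolution before the next dose matters. Check it against Section 4.3 and footnote 7 of the schedule, and add a cross-reference between 3.3.1 and 4.5. Which rule applies is for the sponsor and investigator to decide.

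The cost is about one sentence in one of the two sections, with no new examinations.

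Optionally, since the trial has ended, the safety report can identify any patient who received MDX-010 after an autoimmune ocular event. The listings already planned for dosing (3.1), eye examinations (5.3), adverse events (7.1) and immune-related adverse events (7.2) should be enough for this. It is a reporting preference, and the point does not depend on it.
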